6.3 Interim analysis

An interim analysis to evaluate toxicity will be performed after patient number 20 has completed radiotherapy and has one month of follow-up. An independent interim analysis committee will be

appointed to the task. The study will be stopped if the rate of grade 4 pneumonitis or esophagitis exceeds 15% in the study, or unexpected severe toxicity appears at any time.

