8.2 Expected adverse effect

Tarceva: The most common, expected adverse events for Tarceva include: Rash, pruritus, dry skin, diarrhea, nausea, vomiting, stomatitis, abdominal pain, fatigue, dyspnoe, cough, anorexia, infection, conjunctivitis, and keratoconjunctivitis sicca.

Irradiation: The toxicity of irradiation of NSCLC is determined of the dose and treatment volume of organs at risk. These are as followed:

Organs at risk	Acute (1-12 weeks)	Late >3 months
Lung ¹	Pneumonitis (cough, dyspnoe, fever)	Fibrosis (cough, dyspnoe)
Esophagus ²	Swallowing difficulties, pain	Stenosis (swallowing difficulties)
Heart	Pericarditis ⁴	Fibrosis
Skin	Edema, skin rash	Fibrosis, telangiectasies
Spinal cord	Lhermitte sign ³	Radiation myelitis ⁴ (neurological deficits)

¹: The risk of acute pneumonitis may increase in irradiation when Tarceva is combined with -radiation. The risk of pneumonitis increases with the V₂₀ of the lung. The symptoms may develop before stop of irradiation. The treatment in the case of pneumonitis is steroid ± antibiotics.

² Occurrence of esophagitis is connected to treatment volume and concomitant therapy.

³ Lhermitte sign is a transient self-limiting symptom of radiation impact on the cervical spinal cord.

⁴Pericarditis and radiation myelitis: no cases of these side effects are expected in this study.

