8.3 Management of radiation complications during radiotherapy

In case of grade 3 or worse esophagitis or pneumonitis, the administration of Tarceva will be terminated for that patient.

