8.4 Management of radiation complications

In case of increasing dyspnoe during radiation or within 3 months after cessation of radiation pneumonitis must be suspected. Treatment with steroids is recommended e.g. prednisolone 25-50 mg or higher doses if necessary administered as 1-2 daily doses. Since infection is difficult to rule out, it is recommended to start treatment with antibiotics. Since tumor progression, myocardial infarction, and thromboembolic conditions may occur in these patients, ECG and appropriate biochemistry should be obtained. CT-scan or ECCO of the heart may be necessary.

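### The study-level toxicity stopping rule counts grade 4 pneumonitis or esophagitis only, so as worded fatal cases are left out of the numerator

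*Protocol*

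**What the plan says.** Protocol section 6.3 sets one planned toxicity look by an independent committee: "An interim analysis to evaluate toxicity will be performed after patient number 20 has completed radiotherapy and has one month of follow-up". The stopping criterion follows: "The study will be stopped if the rate of grade 4 pneumonitis or esophagitis exceeds 15% in the study", with a second trigger, "or unexpected severe toxicity appears at any time". No stopping probability is given for either.

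Section 3.3 sets CTC version 3.0 as the grading scale. The protocol does not reproduce that scale.

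For the same two toxicities, section 8.3 uses a grade range that is open upwards for the individual patient: "In case of grade 3 or worse esophagitis or pneumonitis, the administration of Tarceva will be terminated for that patient". Section 8.1 likewise makes every event graded above 3 a serious adverse event, with no upper limit.

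Section 8.2, on expected adverse effects, lists pneumonitis and esophageal symptoms in its irradiation table. A footnote adds that the combination may raise the risk of acute pneumonitis.

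**The concern.** A monitoring rule should become more likely to stop the study as the toxicity gets worse. A numerator limited to a single grade can do the opposite. If an event that would have been grade 4 proves fatal, it leaves the count. Three grade 4 events in 20 patients give 15%, which does not exceed the limit, and any number of deaths from the same two toxicities would not alter that figure.

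These are the two toxicities the sponsor chose to monitor, and for pneumonitis the protocol itself anticipates a possible increase. The committee probably would want to count deaths. A prespecified rule handed to an independent committee should not depend on the committee reading past its wording.

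**Working it through.** **Inputs**
- Threshold: more than 15%, grade 4 pneumonitis or esophagitis (section 6.3).
- Patients at the look: 20 (section 6.3).
- Grading scale: CTC version 3.0 (section 3.3). That death is a grade above 4 is a property of this scale, which the protocol adopts but does not print.
- True combined rate *t* of grade 4 and fatal events, and the fraction *f* of them that are fatal: not in the documents. Both are assumed and varied below.

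**Step 1: the boundary.** 0.15 × 20 = 3. To exceed 15%, at least 4 events are needed. The protocol states no operating characteristic, so there is no figure of its own to reproduce.

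**Step 2: the stopping probability.** With X the number of counted events among 20 patients and *p* the rate of counted events,

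P(stop) = P(X ≥ 4) = 1 − Σ(k = 0 to 3) C(20, k) p^k (1 − p)^(20 − k).

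For p = 0.25 the four terms are 0.0032, 0.0211, 0.0669 and 0.1339. They sum to 0.2252 (the rounded terms add to 0.2251), so P(stop) = 0.775, or 77% (0.7748 before rounding). For p = 0.15 the terms are 0.0388, 0.1368, 0.2293 and 0.2428, which sum to 0.6477, so P(stop) = 0.352.

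**Step 3: literal wording against grade 4 or worse.** If fatal events count, p = t. Under the literal wording, p = t(1 − f). For example, t = 0.25 and f = 0.40 give p = 0.25 × 0.60 = 0.15.

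| Combined rate t | All counted | Literal, f = 10% | f = 25% | f = 40% | f = 50% |
|---|---|---|---|---|---|
| 20% | 59% | 50% | 35% | 21% | 13% |
| 25% | 77% | 69% | 53% | 35% | 23% |
| 30% | 89% | 83% | 69% | 50% | 35% |

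In each row the literal rule loses sensitivity as the fatal share rises. At t = 25% the loss runs from 77 − 69 = 8 points to 77 − 23 = 54 points.

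**Step 4: does the second trigger cover the gap?** It requires the toxicity to be unexpected. Section 8.2 places pneumonitis and esophageal effects under expected effects of irradiation. Section 8.1 defines unexpected, for serious adverse event reporting, by the product's SPC, which is not at hand. Section 6.3 does not say which sense applies, or whether a fatal outcome makes an expected toxicity unexpected. Coverage is therefore unclear: the text neither establishes it nor excludes it.

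**The case against.** **Grade 4 may be shorthand for the top category.** Appendix 4 also ends at a bare grade 4 row, and section 1.2 reports earlier experience as grade 3-4. A reader might infer that the closed wording is peculiar to section 6.3. It is not, so the wording may be loose drafting rather than a decision to exclude deaths. This stands as an account of intent. It does not settle what the rule counts, because sections 8.1 and 8.3 show that the protocol uses open-ended wording when it means a grade and everything above it.

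**Deaths would not go unseen.** The committee evaluates toxicity in general, deaths are serious adverse events reported to the sponsor within one working day, and the second trigger might be invoked. All of this is true. A reader should not infer that the trial would ignore fatal toxicity. The defect is confined to the numerical rule.

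**The size depends on an assumed fatal share.** This also stands. At a 10% share the loss is 8 points, and the large losses need shares of 40% or 50%. The protocol's background gives no reason to expect high rates: no grade 3-4 case of either toxicity in 22 patients, and 9% grade 4 esophagitis in a small chemo-radiotherapy study.

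**Timing.** A reader might also infer that the look comes too early, since patient 20 is seen at one month while section 8.4 says "In case of increasing dyspnoe during radiation or within 3 months after cessation of radiation pneumonitis must be suspected". The documents do not support this as an error:
- One month is the minimum, for patient 20 only. At 57/24 = 2.375 patients a month, the patient enrolled k places before number 20 has 1 + k/2.375 months after radiotherapy. This is under 3 months only for k = 0 to 4, so about 15 of 20 have the full window. Those five have seen about 0.33, 0.47, 0.61, 0.75 and 0.89 of it, and (15 + 3.07)/20 is about 90% overall.
- The acute period in section 8.2 has no stated starting point.
- Section 8.4 is a prompt for clinical suspicion, not an assessment window.
- No visit is scheduled near 3 months after radiotherapy.

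An early look against a more complete one is a trade-off the sponsor may make.

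**Conclusion.** The point holds for the grade wording. As written, the numerical rule in section 6.3 leaves out fatal pneumonitis and esophagitis, and the clause on unexpected toxicity does not clearly bring them back. At a true combined rate of 25%, the chance of stopping at 20 patients falls from 77% to between 69% and 23% as the fatal share goes from 10% to 50%.

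This rests on three assumptions: the rule is applied literally, CTC version 3.0 grades death above 4, and the assumed rates and fatal shares are plausible. The direction of the effect needs only the first two and some fatal events among those that would otherwise count. The documents do not support going further, to a claim that deaths are hidden from the committee or that the one-month look is wrong.

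**What to change.** Reconcile section 6.3 with the open-ended grade wording of sections 8.1 and 8.3, so that the numerator reads grade 4 or worse pneumonitis or esophagitis and fatal events of these two toxicities count. Keep the stated 15% threshold and the look at 20 patients.

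The cost is a change of a few words in one sentence. No extra patients, visits or looks are needed, and events above grade 3 are already collected as serious adverse events. The downside is that the rule fires more often whenever some events are fatal, by the differences in the table above. If no events are fatal, its behavior does not change.

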6.4 Expected time frame of study

The study is expected to recruit patients during a 2-year period starting q2 2009 and ending q2 2011. Analyses of results will be performed 9 months after last patient has been included, and results will be reported. Further analyses may be performed 5 years after the last patient has been included. Each site is expected to include between 3-15 patients.

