1.3 Tarceva

Tarceva (Erlotinib hydrochloride) is a quinazolinamide that inhibits the intracellular tyrosin kinase domain of the EGFR. It is formulated as immediate release tablets. Bioavailability of Erlotinib following a 150 mg oral dose is about 60% (and almost 100% if taken together with food) and peak plasma levels occur 4 hours after dosing. The median half-life is 36 hours, and the time to reach steady-state plasma concentration is 7-8 days (12). Smokers have a 24% higher rate of Erlotinib clearance. Erlotinib is metabolized by the liver cytochrome P450 system primarily by CYP3A4 which may be a cause of interaction with other drugs.

2. Objectives of the study

The trial is a phase II study of daily Tarceva combined with definitive radiotherapy in inoperable locally advanced non small cell lung cancer (stage IIB-IIIB).

The objective of the phase II trial is to examine Tarceva concomitant with curatively intended irradiation 66 Gy (2 Gy x 33 F, 5 F per week):

Primary endpoint

- Local failure free survival at 9 months after start of radiotherapy evaluated at CT scan.

[figure not shown]
Secondary endpoints

- Toxicity
- Local tumor control by CT-scan
- Overall response rate (CR + PR).
- Local tumor control at 9 months evaluated by PET-CT
- Overall survival
- Disease free survival
- Late toxicity

3. Study design and dosing regimen

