3.2 Dosing regimen

Tarceva will start at the day of the radiation in daily dose of 150 mg. The last dose will be given the day the radiotherapy stops. Tarceva will be administered continuously for approximately 6.5 weeks. Drug accountability will be registered according to Good Clinical Practice (GCP). The radiotherapy is only administrated 5 days a week.

3.3 Interruption or discontinuation of Tarceva in the individual patient.

Toxicity grading will be according to the CTC version 3.0. Following dose adjustment for drug-related toxicity is recommended: If any grade III or worse toxicity including skin toxicity or diarrhea occurs, the Tarceva will be paused till toxicity has resolved to a grade II or better. The Tarceva will be resumed in a dose of 100 mg if the dose before pausing was 150 mg, or 50 mg if the dose was 100 mg. If the dose was already 50 mg, the Tarceva will not be resumed. The radiotherapy should be continued. For management of radiation complication during therapy see section 8.2. Management of Tarceva related toxicities see Appendix 4.

4. Planning of radiotherapy

The planning technique is based on ICRU62 recommendations, and the DOLG 2009 criteria. The planning may, however, make use of 4-D scans, and that will influence the margins, se below. The prescribed dose is 66 Gy /33 F / 5 F per week. If induction chemotherapy has been administered radiation may start within 2-5 weeks after last dose of chemotherapy.

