5.3 Monitoring during therapy

The patient may receive induction chemotherapy before inclusion in the study, and is as such not part of the study. The patients cannot be included in the study before a plan has been worked out showing that curatively intended radiation is possible, and informed consent has been obtained (Fig. 1).

	Screening/ Baseline	Treatment Period Timing	Day 30-45 after stop of treatment
Informed Consent	x	-	-
Demographics	x	-	-
Medical history	x	-	-
Physical examination	x	Weekly	x
Body weight	x	Weekly	x
Laboratory ¹	x	Weekly	x
ECG	x	-	x
Lung functions test ²	x	-	x
Lung CO diffusion test	x	-	-
CT scan thorax and upper abdomen	x	-	x
Tumor measurements	x	-	x
PET-CT ³	x	-	-
CT scan brain ⁴	x ⁴	-	-
Performance Status (PS)	x	Weekly	x
Side effects ⁵	-	Recorded weekly	x
Study drug compliance ⁶	-	x	x
Smoking status	x	Recorded Weekly	x

¹ Hematology: Hemoglobin, WBC, granulocytes and platelet count, INR (Only for patients receiving warfarin or coumarin-derivative). Biochemistry: Alkaline phosphatase, Serum bilirubin, Serum creatinine, ALAT (SGPT), LDH. Only laboratory abnormalities linked to unexpected clinical symptoms will be documented in the CRF.

² FEV₁/FVC test. If neoadjuvant chemotherapy, the test must be performed after cessation of chemotherapy.

³ CT scans, PET CT scans per institutional standards, EBUS or mediastinoscopy may be accepted as mediastinal evaluation if PET-CT is not available

⁴ If no PET-CT available

⁵ Side effects to be recorded according to CTC version 3.0

⁶ Pharmacy log

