5.4 Follow-up

The patients will be followed until 5 years after the start of radiotherapy or to recurrent disease according to the follow-up schedule. After discontinuation in the study the patient will be followed according to local standard.

Follow up (± 1 month after start of RT)	6	9	12	15	18	21	24	30, 36, 42, 48, 54, 60
Medical history	x	x	x	x	x	x	x	x
Physical examination	x	x	x	x	x	x	x	x
Laboratory ¹	x	x	x	-	x	-	x	-
Lung function tests FEV ₁ /FVC	x	x	x	x ²	x	x ²	x	x
Lung CO diffusion test	-	x	-	-	-	-	x	-
Weight	x	x	x	x	x	x	x	x
CT scan of thorax and upper abdomen	x	x	x	x	x	x	x	x
Tumor measurements ³	x	x	x	x	x	x	x	-
PET-CT ⁴	-	x	-	-	-	-	-	-
Performance Status	x	x	x	x	x	x	x	x
Smoking status	x	x	x	x	x	x	x	x
Side effects ⁵	x	x	x	x	x	x	x	x

¹ Hematology: Hemoglobin, WBC, granulocytes and platelet count, INR (Only for patients receiving warfarin or coumarin-derivative). Biochemistry: Alkaline phosphatase, Serum bilirubin, Serum creatinine, ALAT (SGPT), LDH. Only laboratory abnormalities linked to unexpected clinical symptoms will be documented in the CRF

² FEV₁/FVC test.

³ RECIST criteria (appendix 2)

⁴ PET CT scans if available at the institution

⁵ Radiation sequelae

5.5 Tumor response criteria.

Although PET-CT is allowed, the tumor response will be evaluated according to RECIST-criteria (version 1.1) by CT-scans of thorax and upper abdomen (15). Suspected recurrent tumor locally or regionally should be verified by biopsy if appropriate.

6. Criteria for efficiency and data-analysis

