6.1 Statistical considerations

All calculations will be performed on the basis of intention to treat. 2 sided tests will be performed. Level of type 1 error is 5%.

6.2 Sample size calculation:

Observed local failure free survival rate after 9 months after initiation of radiation was 70% among 300 patients treated in Odense for NSCLC stage IIB-IIIB. The study will be designed to find local recurrence free survival of 80% at 9 months after initiation of radiation equivalent to about 6-7 months after finishing radiotherapy. A rate of 80% would be clinically interesting, and should be included in the confidence interval of the phase II trial at a power of 90%. This requires 57 patients to be included in the phase II trial.

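### Section 6.4 times the analysis from last inclusion, at least one month before the last patients' month-9 CT windows close

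*Protocol*

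**What the plan says.** - Protocol section 6.4 sets the time of the analysis: "Analyses of results will be performed 9 months after last patient has been included, and results will be reported". Apart from the toxicity interim and optional analyses at 5 years, the protocol gives no other timing.
- Section 2 defines the primary endpoint and its clock: "Local failure free survival at 9 months after start of radiotherapy evaluated at CT scan".
- Section 5.4 heads the visit table, which includes the CT at month 9, with "Follow up (± 1 month after start of RT", read here as one month either side of each visit.
- Section 5.3 puts inclusion after treatment planning and consent: "The patients cannot be included in the study before a plan has been worked out showing that curatively intended radiation is possible". Radiotherapy therefore begins on the day of inclusion or later. The gap is not stated.
- Section 6.1 requires intention to treat, and section 6.5 commits to reporting every included patient, so the last patients enrolled count in the result.

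**The concern.** Two clocks are in use. The analysis date runs from inclusion, while the endpoint runs from start of radiotherapy and carries a tolerance of one month. With the same nominal 9 months on both, the analysis date cannot allow for the gap between the two starting points or for the late half of the scan window. Read literally, section 6.4 has the primary result analysed and reported while some patients can still have their primary-endpoint CT within the rules. Their outcome would then be missing because of the calendar, not because of anything that happened to them. In a single-arm trial of 57 patients, each such outcome moves a crude rate visibly.

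**Working it through.** **Inputs.**
- Sample size 57 (section 6.2: "This requires 57 patients to be included in the phase II trial"). It is reproduced as a 90% interval of half-width 10 points around 70%: 1.645² × 0.70 × 0.30 / 0.10² = 56.8, rounded up to 57. Nothing below depends on that derivation.
- Accrual of 24 months (section 6.4: "The study is expected to recruit patients during a 2-year period starting q2 2009 and ending q2 2011"). Uniform accrual is assumed: 57/24 = 2.375 inclusions a month.
- Month-9 CT window: months 8 to 10 from start of radiotherapy (sections 2 and 5.4).
- Gap L from inclusion to start of radiotherapy: not stated. The main range assumed is 0 to 0.75 month. Section 4 gives an outer limit for some patients: "If induction chemotherapy has been administered radiation may start within 2-5 weeks after last dose of chemotherapy". Because induction chemotherapy precedes inclusion (section 5.3), L for them is at most 5 weeks, or 5 × 7/30.4 = 1.15 months. No limit is given for the others.

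**Dates, counted from last inclusion.** The last patient's nominal month-9 date is 9 + L and the window closes at 10 + L. The analysis is at 9. The shortfall is L months to the nominal date and 1 + L months to the close of the window.

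**Patients affected.**
- Nominal date not yet reached: 2.375 × L.
- Window still open: 2.375 × (1 + L).
- Expected without the CT: a patient included t months before the last one is 9 + t − L months from start of radiotherapy at cut-off. With scan dates uniform over months 8 to 10, the chance of no scan yet is (1 + L − t)/2, capped at 1. Summed over t, this gives 2.375 × (1 + L)²/4 for L up to 1, and 2.375 × L beyond that.

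| L (months) | Nominal date not reached | Window open | Expected without CT |
|---|---|---|---|
| 0 | 0 | 2.4 (4%) | 0.6 (1%) |
| 0.75 | 1.8 | 4.2 (7%) | 1.8 (3%) |
| 1.15 | 2.7 | 5.1 (9%) | 2.7 (5%) |

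**Effect on the result.** One patient is 1/57 = 1.75 points of a crude rate. Over the main range, the expected undetermined part is 0.6 × 1.75 = about 1 point to 1.8 × 1.75 = about 3 points. Precision hardly changes: the 95% half-width at 80% is 1.96 × √(0.16/57) = 10.4 points with 57 patients and 1.96 × √(0.16/55) = 10.6 points with 55.

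**The case against.** **Section 6.4 is a forecast.** Its title speaks of an expected time frame and its recruitment dates are given by quarter, so it can be read as a planning estimate. Sections 6.1 and 6.5 also keep every patient in, so a sensible team would wait for the last scans. This lowers the weight of the point but does not remove it: this sentence is the protocol's only timing for the primary analysis, and it uses the wrong starting point for the endpoint.

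**The scans may be due in time.** With no gap between inclusion and radiotherapy, the last nominal date falls on the analysis date itself. A plan must exist before inclusion, so planning time does not lengthen the gap. This stands: the cut-off comes strictly before the due date only if the gap exceeds zero. The open window of one month remains in every case.

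**An open window is not a missing scan.** This also stands. A reader might take the 4 to 7% with open windows as the share of missing endpoints, but many of those patients will already have been scanned. The expected share is 1 to 3%, and some of these will already have a known failure.

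**A stronger inference, which the documents do not support.** A reader might infer that, because month 9 lies in the middle of the scan window, the reported rate will be inflated by about 5 points against the reference in section 6.2 ("Observed local failure free survival rate after 9 months after initiation of radiation was 70% among 300 patients"). With constant hazard −ln(0.70)/9 = 0.0396 a month and every failure dated at a scheduled scan, a curve read at exactly 9.0 months would indeed give about 75% when the truth is 70%. But the protocol prescribes no such reading. An endpoint evaluated at CT is most naturally status at the month-9 CT, and how scans at months 8 to 10 are counted is ordinary SAP material. The 5 points also require that no event is dated otherwise. If half the hazard were deaths with known dates (an assumption), the reading would be 72.5%. Finally, the protocol does not say how failures were dated in the series behind the 70%, so the same delay may sit in the reference.

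**Conclusion.** The inconsistency is real and follows from sections 2, 5.3, 5.4 and 6.4 alone. The stated analysis date falls 1 + L months before the last month-9 CT window closes: 1.0 to 1.75 months over the assumed range of L, and 2.15 months at 5 weeks. About 2.4 to 4.2 patients have an open window at that date, and about 0.6 to 1.8 would be expected to lack the CT. These counts rest on uniform accrual, an assumed gap of 0 to 0.75 month and scan dates uniform within the window. The consequence is a small, avoidable amount of missing primary data, with no demonstrated direction of bias. It deserves correction because it concerns the sole primary endpoint and costs little to put right.

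**What to change.** Replace the timing sentence in section 6.4 with wording such as: *The primary analysis is performed when the last patient has reached 10 months after start of radiotherapy and all month-9 CTs are entered.* Add to section 2 that the primary result is status at the month-9 CT, done between months 8 and 10. Do not replace this with a Kaplan-Meier curve read at 10 months: set against a 9-month reference, that would count an extra month of events and could add bias of its own.

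The cost is one sentence in each of two sections, and results about 1 to 2 months later.
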